someone uses, though shows improvement with sustained abstinence¹⁶³⁻¹⁶⁵. In fact, longitudinal analyses our team has conducted support the conclusion that PSM occurs in the context of AOD-related declines in academic performance¹⁴⁷. Specifically, increases in alcohol and marijuana use over time appear to contribute to declines in class attendance, which in turn contribute to declines in GPA, and this cascade of events is strongly predictive of students engaging in PSM misuse for studying. In an intervention focused solely on reducing PSM misuse, most PSM misusers would have little room for decreasing their misuse due to the episodic use patterns (primarily around mid-terms and finals). Thus, in addition to directly targeting PSM misuse through a PFI, another reason for this application's significance stems from its focus on reducing PSM misuse directly as well as targeting intervention components for co-occurring alcohol and marijuana misuse (mediators in Studies 2 and 3). We hypothesize that PFI will lead to reductions in comorbid alcohol and marijuana use, and that reductions in alcohol and marijuana use will serve to mediate reductions in PSM misuse. By focusing holistically on the student's underlying substance use problems, an intervention targeting PSM misusers could have a substantial impact on a subset of college students who are at particularly high risk for co-occurring AOD use and associated consequences. Delivery of intervention components will be targeted to high risk times in the academic calendar to maximize benefits.

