
Study 2 Baseline and Randomization: The web-based screening survey will automatically generate an eligibility determination. Students who are ineligible will be shown a message thanking them for their interest in the study and directing them to campus resources that are available to them if they wish to discuss AOD issues. Those meeting the eligibility criteria above will automatically be directed to complete the baseline assessment measures. Once baseline is completed, students will be randomly assigned to either an intervention group (PFI) or assessment only control (AOC) group. Those in the intervention will immediately receive online personalized feedback (see below) on their PSM misuse, academics, and links to alternatives. Over the course of the quarter/semester, students in the intervention group will receive a link to view 4 additional modules surrounding PSM misuse, AOD use, Consequences, and Beliefs/Motives about PSM use. The AOC group will receive a "thank you" screen providing referrals/emergency numbers. Students will be assessed at 6, 12 and 18 months post-baseline using similar email invitations and reminders (expected retention 90% based on past research). Participants will be paid \$20, \$25, and \$30 for each follow-up survey. Students who indicate significant alcohol or drug dependence will be contacted and referred (See Human Subjects). We will make any indicated adjustments/refinements to feedback based on findings prior to *Study 3*.

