Study 3 Recruitment, Randomization & Assessment Procedures: All students who present for services at the University at Albany Health Center and University Counseling Center will be invited to complete a brief, web-based assessment of their PSM and AOD (identical to *Study 2*) in order to assess eligibility for *Study 3* before meeting with their service provider. Routine screening is already part of ordinary clinical practice at UAlbany Health and Counseling Centers, and annually more than 1300 unique individuals visit these centers and complete routine screening. Our own pilot data suggests more than 2/3 of heavy illicit substance users make at least one visit to a campus health clinic annually, indicating these settings are ideal for identifying non-treatment-seeking at-risk PSM users. During the student's medical or counseling appointment, the provider will review the Screening Questionnaire and will refer eligible students to the study using a referral script similar to ones from prior studies successfully conducted in this setting. The same eligibility criteria will be used: students must have misused PSM once or more in the past month and/or 6 or more times in past year.

Students agreeing to participate in the study will be emailed an invitation to log onto a secure web browser,

read a consent statement and indicate their willingness to participate in the study. Those indicating their consent will immediately be routed to the baseline survey which will be used to generate the web-delivered or in-person PFI content and for which they will receive \$20. Following baseline, participants will be randomly assigned to one of three conditions (n = 100 per condition). For Study 3, students will be randomly assigned to either a web-delivered PFI (as in Study 2), a one-session face-to-face brief intervention delivered in an MI style using the PFI as generated in the web condition, or an assessment only control group.

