Participants will complete a battery of web-based follow-up assessments at 6, 12, and 18 months post-baseline for which they will receive \$20, \$25, and \$30, respectively. Participants will additionally complete a brief post-intervention assessment of satisfaction with services and convenience of the intervention, and at each assessment they will be asked whether they have sought other drug treatment since the intervention to control for possible confounding treatment effects. These data will help determine the ideal interventions for the service delivery settings in regard to ease of access and utilization by participants.

Study 3 Training and Ongoing Supervision of Interventionist: One potential method for maintaining or enhancing the efficacy of individual brief interventions for college students seeking campus health and mental health care beyond the life of a research project is to train and supervise existing service providers to deliver the feedback interviews. The current approach will provide training to enhance existing knowledge of the UAlbany Counseling and Health Center staff regarding PSM misuse, and will utilize an existing provider imbedded in the Counseling Center staff at UAlbany to provide the in-person interventions. The provider will complete specific additional training related to both the MI process and PSM, alcohol, and marijuana content of the proposed intervention, and will participate in weekly supervision meetings with Drs. [name] and [name]. In addition, all intervention sessions will be audio-recorded and reviewed for adherence to the protocol and MI competence using existing protocols developed for use in prior funded projects at UAlbany and UW. The interventionist will also complete an adherence checklist after each individual session, to indicate which components were covered in each intervention session. Scores on adherence/competence measures and checklists will be reviewed and included as a covariate in secondary analyses of intervention efficacy.

Measurement and Assessment Procedures: Measures will be completed via a secure web survey, using DatStat Illume and will last 30-45 minutes. Measures selected are in Appendix A.

PSM Measures		
PSM Use	DV	
 PSM Timeline Followback (TLFB) - Quantity and past-30-day frequency of PSM misuse¹⁸⁸ Medical Use, Medical Misuse, and Non-Medical Use Questionnaire^{23, 80}

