Prescription Stimulant Medication Misuse PFI. The intervention is comprised of personalized feedback presented in text and graphic format, and each component is followed by a link to tips for making changes if and when the participant is contemplating or ready to commit to change. These tips will include general relapse prevention strategies, as well as information about the importance of regular class attendance, study habits, and sleep habits for academic success. General educational tips/strategies for time management, as well as initiating behavior change will also be included. The first component of the feedback targets **PSM and academics**, including student's own prescription stimulant use frequency, satisfaction with academic progress and grades, factors identified by the student as interfering with academic performance, sense of their time management and study skills, impact of alcohol and marijuana use on academic/cognitive factors, student-identified actions that could improve academic success, and resources for getting assistance with academic support. The second component targets **PSM and perceived norms**, including perceived and actual past year use, perceived and actual past-quarter/semester frequency, requests to divert PSM (both requests to others and to themselves), perceptions surrounding diversion, attitudes about helping others, and what the science shows about academic impact. By building a discrepancy between student's own PSM misuse and that of others, as well as correcting their perceptions of other's use (norms reduction) and beliefs about PSM, the intervention will reduce PSM misuse. This component ends with campus-specific resources for assessment and support. Component three addresses **PSM and unwanted effects**, with a review of consequences related to PSM use, the science behind PSM misuse, and a link to alternative strategies. In the fourth component, **Reasons/Motives for using PSM** are addressed, including when during the academic year the student tends to use, motives for PSM use, and reasons to limit/avoid use. The final component reviews **Alcohol, Marijuana, and Drug Interactions**. For marijuana use, participants will receive personalized feedback about frequency of use, consequences, and perceived norms; for alcohol use, they will receive information on frequency, quantity, norms, BAC and related effects, and consequences. The section ends with information on drug interactions. Appendix B includes a draft of proposed feedback, to be refined and programmed during the start-up phase.

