Aim 1: To examine whether perceived norms of PSM differs from the “actual” prevalence as estimated by the screening sample, the actual prevalence will be subtracted from the perceived prevalence. A one-sample t-test will be used to assess whether the difference score is statistically significantly greater than 0. If the difference score is a non-normal distribution, we will instead use a non-parametric Wilcoxon sign rank test.

Aim 2: Evaluate efficacy of interventions. We will first examine effects of the intervention on perceived norms, benefits of PSM, and use of alternative strategies as separate outcomes using linear mixed models (a.k.a. hierarchical linear or multilevel models¹²⁰). This project will have 5 repeated measures, yielding up to 6,000 Level 1 observations (repeated-measures) across 1,200 Level 2 (people). The following equation represents a basic analytic model for Aims 2 and 3:

$$\text{Level 1: } Y_{ti} = \pi_{0i} + \pi_{1i}(\text{Post})_i + \pi_{2i}(\text{Month6})_i + \pi_{3i}(\text{Month12})_i + \pi_{4i}(\text{Month18})_i$$

$$\text{Level 2: } \pi_{0i} = \beta_{00} + \beta_{01}(\text{Tx})_i + \beta_{02}(\text{Site})_i + r_{00i}$$

$$\pi_{1i} = \beta_{10} + \beta_{11}(\text{Tx})_i + \beta_{12}(\text{Site})_i$$

$$\pi_{2i} = \beta_{20} + \beta_{21}(\text{Tx})_i + \beta_{22}(\text{Site})_i$$

$$\pi_{3i} = \beta_{30} + \beta_{31}(\text{Tx})_i + \beta_{32}(\text{Site})_i$$

$$\pi_{4i} = \beta_{40} + \beta_{41}(\text{Tx})_i + \beta_{42}(\text{Site})_i$$

where *Post*, *Month6*, *Month12*, and *Month18* are dummy codes for follow-up visit such that the reference time point is baseline; *Tx* represents randomly assigned treatment condition; *Site* represents the study site; *i* indexes participants; *r_{00i}* represents a random effect for the intercept; and *Y_{ti}* represents the outcome for each individual, *i*, at each time, *t*. $\beta_{11} - \beta_{41}$ are primary coefficients as they compare treatment conditions for the difference in the outcomes from baseline to each of the follow-up visits. The model assumes conditional independence, given random-effects and (multivariate) normality of Level 2 random-effects. As additional analyses, we will also specify time as a continuous variable in order to assess differences between intervention and control groups in slopes over time.

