We will then examine effects on PSM, marijuana, and alcohol use and consequences. These outcomes are integers, bounded at zero, and often times positively skewed. Because of potential violations of regression assumptions that can arise due to the non-normal distribution, we will use a generalized form of the linear mixed model (GLMM) with a Poisson distribution in order to more appropriately model these outcomes as counts¹¹⁷. Count regression coefficients are connected to the outcome via a natural log link and are commonly exponentiated (e^β) to yield rate ratios (RRs) describing the proportional increase in the outcome for a 1-unit increase in the predictor (e.g., Treatment (1) compared to Control (0)).

To assess mediation hypotheses, we will utilize an approach that has been used by co-investigators with similar data to the proposed study¹⁹⁷. Kenny et al.¹⁹⁸ described mediation using multilevel models for longitudinal treatment data similar to the present data. Specifically, Kenny et al. focused on change in the direct treatment pathways from a model without the mediator to a model with the mediator (i.e., the common c and c' pathways in the mediation literature). In the present context, that is the treatment cross-level interactions with time ($\beta_{11} - \beta_{41}$) for the model presented above compared to one in which mediators are included as Level 1 time-varying covariates. We will use this approach and consider the percent reduction in effects after the mediator is included in the model. In Neighbors et al¹⁹⁹, this approach was extended using a nonparametric bootstrap¹⁹⁹ to allow estimation of the indirect path without making normality assumptions on the sampling distribution of the indirect effect. Perceived benefits and norms of PSM, use of alternative strategies, and alcohol and marijuana use will be included as the Level 1 time-varying mediators of interest and PSM use and consequences will be modeled as the outcomes. To assess moderators of efficacy, we will include level 2 covariates for baseline levels of motivations of PSM and demographic characteristics as well as their interactions with treatment in the GLMM.

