Aim 3: Efficacy of in-person and web-based interventions. GLMM Poisson regression will be also used to test the efficacy of the web-based PFI and in-person MI on reducing PSM use and consequences. Using the basic model equation, dummy variables rather than a single treatment indicator will be included as Level 2 covariates for web-based PFI and in-person MI such that the reference will be the control group. In addition to comparisons of the two intervention groups to the control, we will also conduct post-estimation general linear contrasts to compare effects of the web-based PFI and in-person MI on the PSM outcomes.

Missing data and attrition. Our prior research has been successful at retaining participants with 85-93% retention over 6 months or longer. GLMMs provide unbiased estimates in the presence of missing data as long as it can be considered ignorable. Missing data are ignorable if they are either missing completely at random or missing at random after accounting for measured variables in analysis, including outcome at earlier time

points¹²⁰. As seen in previous studies, little efficiency is lost in GLMMs with 10%-20% missing data.

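### The Poisson mixed model's standard errors are right only if each student's misuse rate stays fixed; participant-clustered standard errors remove that dependence at little cost

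*Combined protocol and SAP*

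**What the plan says.** The only model equation is under Aim 2 of Data Analysis and serves Aims 2 and 3. It has one random term, the person intercept. The plan adds: "The model assumes conditional independence, given random-effects and (multivariate) normality of Level 2 random-effects". The treatment-by-visit coefficients (Post and months 6, 12 and 18, each against baseline) are named as primary.

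For use and consequences of PSM, marijuana and alcohol, "we will use a generalized form of the linear mixed model (GLMM) with a Poisson distribution". Aim 3 repeats this: "GLMM Poisson regression will be also used to test the efficacy of the web-based PFI and in-person MI on reducing PSM use and consequences". The reason given for Poisson is that the outcomes are skewed non-negative integers; their variance is not discussed. No overdispersion term, visit-level random effect or robust standard error appears. The only bootstrap is for the indirect effect in the mediation analysis. Distributions will be examined first, but no action follows from that for the count outcomes.

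The PSM timeline measure covers "Quantity and past-30-day frequency of PSM misuse". On timing of use, the section on alcohol and marijuana as mediators says "most PSM misusers would have little room for decreasing their misuse due to the episodic use patterns (primarily around mid-terms and finals". The fourth feedback component covers motives, "including when during the academic year the student tends to use". On follow-up in Study 2: "Students will be assessed at 6, 12 and 18 months post-baseline using similar email invitations and reminders". On entry to Study 3: "All students who present for services at the University at Albany Health Center and University Counseling Center will be invited".

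Under Power, 200 datasets per run were generated from the same equation and fitted with the same model. Stated power is above 0.80 for a coefficient of -.13 with 600 per arm, and .80 or higher for -.3 with 100 per arm.

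**The concern.** A person intercept absorbs stable differences between students. It does not absorb one student's rate changing from one 30-day window to the next. Which contrasts are exposed depends on the kind of change:

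- **Irregular change** exposes every visit. One possible source is response date: with invitations and reminders, a look-back window can overlap exams by different amounts for different students and visits.
- **A stable student-specific calendar pattern** exposes 6 and 18 months. It cancels at 12 months, when the season matches baseline.
- **Peaks shared by all students at a visit** are absorbed by the visit terms. In Study 3 students enter when they present for care, so a shared peak can fall at different visits for different students and then acts like a calendar pattern.
- **Post** is exposed if its look-back window differs from baseline's.

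If such variation is large enough, nominal 5% tests of the primary coefficients reject too often, and an ineffective intervention could be declared effective. The power simulation cannot reveal this, because its data contain no such variation.

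**Working it through.** **Inputs from the documents:** 600 and 100 per arm; coefficients -.13 and -.3; p < .05 (two-sided assumed); a 30-day window; follow-up at 6, 12 and 18 months. **Assumptions:** mean 30-day count 1.0 to 3.2 (Study 2) or 1.0 to 3.8 (Study 3); intercept variance 0.25 to 1.0; the form and size of within-student change.

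**1. Model standard error.** With complete data, arm-by-visit terms and no site terms, and with S the total count in an arm at a visit, the estimate is log(S1t/S10) - log(S0t/S00). Its model variance is 1/S1t + 1/S10 + 1/S0t + 1/S00, whatever the intercept variance. As a check, the full model with site terms was fitted to uncapped counts with a strong calendar pattern (log-rate variance 0.25). Rejection under the null was .225/.038/.218 at 6/12/18 months, against .199/.048/.217 from the closed form. With 90% retention it was .217/.050/.205. This confirms the structure; the sizes are for uncapped counts and are not used below.

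**2. The plan's power.** It cannot be reproduced outright, because no PSM mean is given. The mean that yields 0.80 under a pure Poisson model can be back-solved (1.96 + 0.84 = 2.80):

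- Study 2: (3 + e^.13)/(600m) = (.13/2.80)^2, so m is about 3.2.
- Study 3: (3 + e^.3)/(100m) = (.3/2.80)^2, so m is about 3.8.

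The plan states its power as a minimum, so these are approximate lower bounds for the means it used. The larger Study 3 value agrees with the higher intercept that the plan describes.

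**3. Break-even for capped day counts.** Take n = 30 days, mean daily probability p and within-student CV c. The variance is np + np^2[(n-1)c^2 - 1]. It equals the Poisson variance np when c = 1/sqrt(29) = 18.6%. Below that the planned test is conservative under irregular change; above it, anti-conservative. In a calendar pattern the baseline and 6-month multipliers move in opposite directions, so the variance of their difference is 4c^2 rather than 2c^2. Break-even is then c = 1/sqrt(59) = 13.0%, a swing of 1.13/0.87 = 1.3-fold.

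Exam overlap: let k be uniform on 0 to 14 days (mean 7, SD 4.32) and the rate 1 + (r-1)k/30. For r = 3, CV = 0.288/1.467 = 19.6%. For r = 5, CV = 0.576/1.933 = 29.8%.

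**4. Type I error of the planned test, capped day counts, simulated over the assumed ranges:**

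| Assumed change in a student's rate | CV | 6 and 18 months | 12 months |
|---|---|---|---|
| None | 0 | 2-5% | 2-5% |
| Exam days 3x, overlap 0-14 days | 20% | 4-6% | 4-6% |
| Exam days 5x, overlap 0-14 days | 30% | 5-11% | 5-11% |
| Irregular doubling in half the windows | 33% | 6-11% | 6-11% |
| Calendar, 1.25x, even split (600 per arm) | 11% | 3.6-5.1% | about 2-5% |
| Calendar, 1.5x, even split | 20% | 5-9% | about 2-5% |
| Calendar, 2x, 15/85 split (600 per arm) | - | 6.6-11.7% | about 2-5% |
| Calendar, 2x, even split | 33% | 8-20% | about 2-5% |

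**5. The alternative.** The clustered sandwich variance is the sum over arms and participants of (y_t/S_t - y_0/S_0)^2. Type I error was 4.3-5.9% at 600 per arm. At 100 per arm it was 4.9-6.8% uncorrected, and 4.5-5.4% with a leave-one-participant-out jackknife and a t reference on 198 df.

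**6. Power with valid standard errors, at the back-solved means:**

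| Rate | Study 2 | Study 3 |
|---|---|---|
| Constant | .86-.87 | .84-.87 |
| Irregular doubling | .61-.70 | .58-.68 |
| Calendar, 2x, even split, 6 and 18 months | .45-.56 | .42-.55 |

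The calendar pattern costs no power at 12 months. The detectable rate ratio moves from .89 (constant) to .85-.86 (irregular doubling) in Study 2, and from .76-.77 to .69-.71 in Study 3. Near the 18.6% break-even the Poisson variance is right, so power stays close to the plan's .80.

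**The case against.** The strongest reply concerns size. With a constant rate the 30-day cap makes the planned test conservative, so without further change the error runs the safe way. The mechanism closest to the documents is response date combined with exam peaks. It gives essentially nominal error when exam days carry three times the usual rate, and modest inflation at five times; both factors and the even 0-14 day spread are assumptions. The documents describe peaks around mid-terms and finals, which recur each term and are largely shared, so the visit terms absorb them when students share a baseline date. The feedback item on time of year describes intervention content; it is not evidence that half the students peak in opposite seasons. The plan also calls its equation basic and foresees distribution checks, so a refinement is not excluded.

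All of this stands as a limit on size. A reader might infer that the standard errors are too small whenever a student's use varies, or that false-positive rates near 20% are to be expected. The documents support neither: the first ignores the cap and the break-even, and the second needs a 2-fold, evenly split calendar pattern that they do not describe.

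The reply does not remove the gap. No refinement is written for the primary coefficients, and checks without a stated consequence leave the choice of standard error until after the data are seen. The cap also gives no cushion to uncapped counts such as quantity.

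**Conclusion.** The point holds in conditional form. As written, the count models give correct standard errors for the primary coefficients only under conditional Poisson variation around a fixed personal rate. For capped day counts the planned test can be conservative (about 2-5%) or anti-conservative: up to about 11% in the irregular-change settings examined, and 8-20% at 6 and 18 months under a 2-fold, evenly split calendar pattern. Every size rests on assumed means, intercept variances and within-student variation. The 30-day window is stated for the timeline use measures; windows for the consequence scales are not given.

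The stated power holds only without such variation. A reader might go further and call the studies underpowered. The documents do not support that, because the simulation's mean is not stated and the means used here are back-solved.

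This should be fixed because the remedy is cheap and works in either direction. Confidence in the structural point is good; confidence in its size is low to medium.

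**What to change.** Keep the Poisson GLMM point estimates. Add to the SAP: *For PSM, marijuana and alcohol counts, inference on the treatment-by-visit coefficients will use participant-clustered sandwich standard errors, in Study 3 with a small-sample correction (leave-one-participant-out jackknife variance and a t reference).*

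Switching to a negative binomial GLMM with its own standard errors would not do the same job. Under a calendar pattern, at means 3.2 and 3.8, it gave 7.1-8.7% at 6 months and 0.1-1.2% at 12 months.

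Rerun the power simulation with a stated PSM mean, the 30-day cap and a stated range of within-person variation that includes none, analysed with the new standard errors. Restate the detectable rate ratios for Studies 2 and 3.

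The cost is one SAP sentence, modest programming (somewhat more for the Study 3 correction) and a repeated simulation. Data collection does not change. If within-student variation is present, intervals widen and the stated detectable effect becomes less favourable. If the rate is constant, intervals for capped counts become slightly narrower.

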Mediators: Alcohol and Marijuana Comorbidity with PSM Misuse. Given the high correlation between PSM misuse and AOD, it is possible to conceptualize motives for PSM misuse as related to consequences of AOD. For students who report partying motives for PSM, the relationship between AOD use and PSM misuse is intuitively obvious in light of a shared propensity hypothesis. In some cases, students are seeking feelings of euphoria or a buzz from PSM^{1, 145} just as they do with other substances. In other cases, the appeal of PSM is in its ability to deliver wakefulness, which allows the user to extend a drinking session and thereby consume more alcohol^{1, 147}. Yet even when the motives for PSM misuse appear to be purely academic, PSM misuse may still be closely linked to AOD use as a compensatory strategy, whereby students turn to PSM in hopes of making up for the classes and study time they missed as a result of their AOD use, or possibly to manage side-effects of their alcohol and/or marijuana use. In the context of the college setting, heavy alcohol use has been associated with lower GPA, less engagement with faculty, and increased sleepiness¹⁶⁰⁻¹⁶²; conceivably, PSM could be used to combat and counter problems with fatigue and tiredness. Marijuana use is associated with deficits in attention, concentration, and memory, and this impact is more pronounced the more frequently

[figure not shown]

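### Un-lagged mediators mean the planned c to c′ reduction cannot separate lower drinking reducing stimulant misuse from the reverse path or a shared cause

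*Combined protocol and SAP*

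**What the plan says.** The mediation method is given under Data Analysis, Aim 2. The treatment-by-time coefficients (β11 to β41) are estimated once without mediators and once in a model where "mediators are included as Level 1 time-varying covariates". The analysts will then "consider the percent reduction in effects after the mediator is included in the model". A nonparametric bootstrap is added "to allow estimation of the indirect path without making normality assumptions on the sampling distribution of the indirect effect". The mediators are perceived benefits, norms, alternative strategies, and alcohol and marijuana use. The outcomes are PSM use and consequences.

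The hypothesis, under Mediators: Alcohol and Marijuana Comorbidity with PSM Misuse, is that "reductions in alcohol and marijuana use will serve to mediate reductions in PSM misuse". The section on in-person feedback expects the same mediators in Study 3.

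That Mediators section also describes the opposite path for some users: the wakefulness PSM gives "allows the user to extend a drinking session and thereby consume more alcohol". It refers to a shared propensity as well, which is a common-cause account.

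The measures table lists "Quantity and past-30-day frequency of PSM misuse" for the outcome and the same past-30-day window for the alcohol and marijuana timeline follow-back. No section states a lag, adjustment for earlier PSM misuse, a reverse-direction model or a sensitivity analysis. The plan never says that mediator and outcome come from the same wave. That is the natural reading of an un-lagged Level 1 covariate in a model for the outcome at time t, and nothing in the document contradicts it.

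**The concern.** Randomization protects the effect of treatment on PSM misuse and on each mediator. It does not protect the association between mediator and outcome, and the c to c′ comparison depends on that association. If mediator and outcome come from the same wave and the same 30 days, the model cannot tell which moved first. A drop in PSM misuse that lowers drinking, or a common influence that lowers both, leaves the same trace as the hypothesized pathway. The bootstrap deals with the sampling distribution of the indirect effect, not with its direction.

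At stake is a stated hypothesis of Studies 2 and 3. A positive result could be published as evidence that reducing alcohol use is how the intervention works, when the data would fit the opposite account as well.

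**Working it through.** **Inputs from the document.** Study 2 has 600 per arm and a treatment-by-time coefficient of −.13; Study 3 has 100 per arm and −.3 (Power). The outcome model is a Poisson mixed model with log link and random intercept (Aim 2). Study 2 follow-up is at 6, 12 and 18 months.

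**Assumptions, because the document gives no values.** Mean PSM count 3 (3.8 for 100 per arm); mean drinks 8; random-intercept SD 0.8; mediator entered as log(1 + drinks); elasticity of drinks on PSM misuse 0.25 to 0.8; baseline plus three follow-up waves.

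**1. The plan's own figure.** The point disputes no stated number, but the power claim helps anchor the mean count. With person effects conditioned out, var(b) ≈ (3 + e^|b|)/(n·μ). For n = 600, b = −.13, μ = 3: var = (3 + 1.139)/1800 = 0.00230, SE = 0.048, z = 2.71, and two-sided 5% power is 0.77. Power of 0.80 needs μ of about 3.2 (about 3.8 for Study 3). The assumed counts are therefore compatible with the stated power, which cannot be reproduced exactly because its inputs are not given.

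**2. Algebra in the simplest linear case.** Let treatment act on PSM misuse, Y = τT + u, and let drinking only respond, M = γY + e. Regressing Y on T and M gives c′ = τ(1 − r²), where r is the within-arm correlation of Y and M. True mediation is zero, yet the apparent share mediated is r²: 9% at r = .3, 16% at .4, 25% at .5. This is not a general rule. In a random-intercept fit with no person-level component in the mediator noise, the reductions were 5%, 11% and 15%. Regressing M on T and Y instead gives a treatment coefficient of zero, so the reverse-direction model removes the whole effect on drinking. That contrast is why fitting both directions is informative, although measurement error would blur it.

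**3. Poisson simulation.** Drinking has no effect on PSM misuse in any row. Fits are conditional Poisson with a percentile bootstrap of the wave-averaged indirect effect, 50 to 100 data sets per row.

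| Setting | False reduction | Bootstrap excludes 0 |
|---|---|---|
| b = −.13, 600 per arm, elasticity 0.25 | 7% | 17% |
| same, elasticity 0.5 | 23% | 35% |
| same, elasticity 0.8 | 48% | 59% |
| b = −.30, 600 per arm, elasticity 0.5 | 22% | 89% |
| b = −.30, 100 per arm | 22% | 36% |
| shared time-varying cause, b = −.13 | 41% | 66% |
| no link between PSM misuse and drinking, b = −.13 | under 1% | 6% |
| no treatment effect | not meaningful | 6% |

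The random-intercept Poisson model agrees. At b = −.13, c = −0.119 and c′ = −0.097 (19% apparently mediated), with a mediator coefficient of 0.55 where the truth is 0. The shared-cause setting gives 35%.

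**4. Linear check, pure reverse causation, 600 per arm.** False reductions were about 8% at r = .3 and 24% at r = .5. The bootstrap was significant in 41% and 75% of trials for an assumed .25 SD effect, and in 33% for .13 SD at r = .5. Other linear runs, differing in assumed noise structure and effect size, ranged from 13% to 95%. The detection rate is therefore an order of magnitude only.

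**5. Does lagging solve it?** On the reverse-causation data of step 3, a lagged mediator with prior PSM misuse and baseline mediator as covariates gave reductions of −0.1% to 0.5% (for example c = c′ = −0.117). Under genuine same-wave mediation, however, a lagged test was significant in only 5% of linear trials when PSM misuse and mediator were equally stable within person. When PSM misuse was the more stable, the estimate had the wrong sign in 100% of trials. Adding the baseline mediator as a covariate produced significant wrong-sign effects in 28 to 90% of linear reverse-causation trials when the mediator noise had a person component.

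**The case against.** The method is a published multilevel approach that co-investigators have used before, and its timing details may lie in cited papers that are not available here. The protocol cites the team's own longitudinal work in support of alcohol and marijuana use leading to PSM misuse, and it tests treatment effects on the mediators separately. The explicit reverse path concerns alcohol, and only some users.

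Part of this stands. Same-wave timing is inferred, and the reverse path is documented for alcohol alone. For marijuana, norms, perceived benefits and alternative strategies it is plausible but not described. The rest does not answer the point: prior use of a method does not change its algebra, and background studies cannot establish direction in this trial's data.

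Three stronger readings are tempting and unsupported. A reader might infer that the analysis is bound to declare mediation. It is not: the false reduction needs a treatment effect and a link between PSM misuse and mediator, and significance is then a matter of probability. A reader might infer that a positive result would count for nothing. It would be consistent with the hypothesis, but would not show direction. A reader might infer that a lagged model should replace the planned one. Step 5 shows why not: windows of 30 days, waves six months apart and use the protocol calls episodic suit a lagged model poorly.

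**Conclusion.** The concern holds in this form: as written, the c to c′ reduction with its bootstrap cannot distinguish the hypothesized pathway from the reverse path or a shared cause, and no other part of the plan does so. The expected direction of the bias, toward apparent mediation, was the same in every reverse-causation and shared-cause setting examined. Its size is not fixed: roughly 7 to 48% apparent reduction, with significance in about 17 to 89% of trials across the main settings. Both ranges rest on assumed counts, variances, elasticities, correlations and effect sizes. With no treatment effect, or no link between PSM misuse and drinking, false significance stayed near nominal (6%). The point is firmest for alcohol. It limits what the mediation results can support; it does not touch the randomized treatment contrasts of Studies 2 and 3.

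**What to change.** Keep the concurrent analysis, but state in the SAP that its reduction is an association that does not establish direction. Alongside it, on waves already collected, fit:

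- a lagged model, with the mediator at 6 months predicting PSM misuse at 12 months and the mediator at 12 months predicting 18, adjusted for earlier PSM misuse;
- the reverse-direction model, with PSM misuse as mediator of alcohol and marijuana use.

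Claim directional mediation only where the forward models support it and the reverse model does not explain the data equally well. Do not make the lagged model the sole basis, and state in advance that a null or wrong-sign lagged result is not evidence against mediation.

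The cost is SAP wording, modest extra analysis and more cautious conclusions. The 6-month outcome has no earlier follow-up mediator, so it gets no lagged test. The model equation includes a post-intervention wave that might supply one, but the Study 2 procedures list only 6, 12 and 18 months, and the post-intervention assessment described for Study 3 covers satisfaction and convenience. Those sections should be reconciled.
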